### **Sub-studies 1a and 1b**

Once enrolled, all study participants will receive a package containing the following:

- 14 day supply of study medication (capsules containing either FoTv or mQFPD or placebo)
- Digital thermometer
- Urine pregnancy test (for women of child bearing potential)
- Written instructions on proper usage of study medication
- Paper study daily diary, to include daily medication diary, symptom scores, and temperature/BP measurement data
- A blood pressure cuff or glucometer will be provided to study subjects who require but do not possess one. The study participants are not responsible for lost, stolen, or damaged devices

The study package will be sent via local courier or phlebotomist who will coordinate directly with the study participant to complete delivery. Missed doses will be logged in the provided medication diary, remain unused, and be accounted for at the end of the study. Participants will continue to make every effort to maintain quarantine through vigorous hand washing and appropriate self-isolation measures. All study participants will also receive instruction to strictly avoid alcohol, cannabis, and dairy products during the study period.

During the trial period, participants will be verbally instructed on proper usage of study product, asked to take their temperature twice daily until they reach two consecutive afebrile readings. Participants with prior hypertension will also be required to take daily home measurements of their blood pressure and report any measurements of SBP <90 or >150, or DBP >90 directly to the study team. Any measurements of SBP below 80 or above 180 will be advised to seek immediate medical attention (as specified in Section 15). Participants with prior diabetes will take daily morning glucose measurements and report any blood glucose measurement >200 directly to the study team. Any measurements of blood glucose below 70 will be advised to eat a carbohydrate rich food and report to the study team, and measurements persistently below 70 will be advised to seek immediate medical attention as an immediate priority prior to reporting to the study team. Participants with congestive heart failure or using diuretics will take daily morning weight measurements using a home scale and report to the study team any weight change greater than 3 lbs (1.5 kg) during the study period.

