### 5. Vital Signs (to be collected for participants of sub-studies 1a and 1b only):

- Body temperature will be self-reported at Study Treatment Day 1, daily throughout the treatment period until two consecutive afebrile results are seen, and again at the End of Study Treatment Day 14.
- Study participants with a baseline diagnosis of hypertension will be instructed to take daily blood pressure measurements using a home blood pressure cuff. If they do not have access to a home blood pressure cuff, members of the study team will purchase one online and have it sent next-day. They are to contact the study team with any measurement of systolic blood pressure above 150 or below 90, as well as diastolic measurements above 90. Any measurements of SBP below 80 or above 180 will be advised to seek immediate medical attention as specified in section 15.
- Study participants with a baseline diagnosis of diabetes mellitus who are on insulin or sulfonylureas will be instructed to take blood sugar measurements in the morning, as well as three times daily before meals. If they do not have access to a home glucometer, members of the study team will purchase one online and have it sent next-day. Any measurements of blood glucose below 70 will be advised to eat a carbohydrate rich food and report to the study team, and measurements persistently below 70 will be advised to seek immediate medical attention as an immediate priority prior to reporting to the study team.
- Study participants with a baseline diagnosis of congestive heart failure or diuretic use will be required to monitor their weight daily and notify the study team if their weight changes by greater than 3 lbs (or 1.5 kg) throughout the 14 day trial period. If they do not have access to a home scale, members of the study team will purchase one online and have it sent via next-day delivery.
- Study participants who are not hospitalized yet remain febrile and report ongoing symptoms at EOT visit (Day 14) will continue to take their temperature and be contacted every 2-3 days by members of the study team until they are no longer symptomatic and are afebrile.

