### Test Product Dose and Route of Administration

Participants in sub-studies 1a and 1b: The dosage of FoTv or mQFPD is 8 capsules three times a day for 14 consecutive days. It does not need to be consumed with food. It is best taken at least 30 minutes before OR at least 60 minutes after meals, in the morning, noon and evening. Accidentally missed doses will not need to be taken at a later time, but will be recorded in a daily diary. Should swallowing capsules be an issue, they can be opened and dispensed into water or juice for easy ingestion.

Participants in sub-study 1c: The dosage of FoTv is 8 capsules three times a day for 4 consecutive days ((starting with the day of the first vaccination). It does not need to be consumed with food. It is best taken at least 30 minutes before OR at least 60 minutes after meals, in the morning, noon and evening. Accidentally missed doses will not need to be taken at a later time, but

will be recorded in a daily diary. Should swallowing capsules be an issue, they can be opened and dispensed into water or juice for easy ingestion

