### Inclusion Criteria

1. Positive COVID-19 diagnosis within the prior 72 hours or within 9 days of symptom onset
2. Age 18 and older

3. Women of childbearing potential must have a negative urine or serum hCG. Women of childbearing potential must have a negative serum pregnancy test at screening and agree to use contraception throughout the study period.
4. Capable of documenting vitals, symptoms, and study product intake daily and communicating this information to the study team
5. Willing to avoid alcohol, cannabis and dairy products during the study period.

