#### *Effects of upregulation of IL-1-β and IL-6 on COVID-19 disease progression*

Concern has been raised regarding isolated polysaccharide extracts and induction of IL-1B, an inflammatory cytokine that may exacerbate the runaway inflammatory presentations in later stages of the COVID-19 disease (Alschuler et al., 2020). Polysaccharides in mushrooms have been shown to initiate an immune response, sparking activity of TNF- $\alpha$ , IL-1B, IL-6, and other pro-inflammatory proteins involved in acute immune activation. However, other biologically active compounds in mushrooms and mycelium (such as the sterols, phenols, and other terpenoid compounds) are important for the resolution of this inflammatory response, inducing anti- inflammatory cytokines such as IL-10 and

IL-1ra (Davis et al., 2020, Davis et al. 2020 unpublished). Therefore, an unextracted whole mushroom mycelium complex impacts the immune system in a more balanced and modulatory manner.

Nevertheless, in its review of the IND application for this study, the FDA raised the following as a non-clinical hold issue regarding FoTv:

*Because FoTv may stimulate immune function, we are concerned these products may accelerate the development or exacerbate the magnitude of COVID-19, a disease that is typically associated with excessive or aberrant host immune responses (i.e., cytokine storm). Specifically, we are concerned about the in vitro finding that Fo robustly upregulates cytokines IL-1-β and IL-6 ranging from 8,000- to 145,000-fold. Please further explain this finding and how it translates clinically, particularly in the context of COVID-19 and the risk of accelerating or exacerbating disease progression.*

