While IL-1-β and IL-6 upregulation effects have been observed with aqueous extracts of Fo in vitro, these findings warrant additional context and explanation for COVID-19 clinical studies. Firstly, these pro-inflammatory immune protective cytokines are being discussed in the context of monoclonal antibody treatment for COVID-19: IL-1 $\beta$ , IL-6, and TNF- $\alpha$ . Secondly, the non-overlapping, post-aqueous ethanol extraction showed a decrease in IL-1-β and IL-6, demonstrating complex and differential effects on immune system functioning. While Fo aqueous fractions increased levels of pro-inflammatory and immune activating cytokines, it also triggered robust increases in the anti-inflammatory cytokines IL-10 and IL-1ra (as did Tv). These dual and opposing effects by different fractions of Fo may suggest a ‘regulating’ effect in vivo.

Fo has triggered the expression of cytokines relevant to other facets of viral pneumonic disease. Eotaxin is involved in the inflammatory recruitment and infiltration of eosinophils and other phagocytic cells to the lung tissue. The antiviral peptides IFN- $\gamma$ , MIP-1 $\alpha$ , and MIP-1 $\beta$  are currently being discussed in the context of SARS-CoV-2 infections, and whether high or low levels are beneficial or detrimental. IL-4, also upregulated by Fo, has protective effects in influenza, SARS, and pneumonia.

In terms of predicting potentially adverse clinical responses to FoTv, we are encouraged by the lack of reported adverse effects of these products pertaining to the exacerbation of viral infection during cold & flu season, which have sold hundreds of thousands of units over the past decade. While post market adverse effects reports are not considered to be high-quality evidence, they offer additional context into overall product safety and tolerability in a consumer population.

It is also worth mentioning that these effects were observed in PBMC cells from healthy donors. The clinical effects of FoTv in COVID-19 patients are unstudied and an adverse effect may present. We have relied on the Phase 1 safety study to monitor for any adverse effects that may result from FoTv administration.

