## **17. POTENTIAL BENEFITS**

For the study participant, FoTv and mQFPD may potentially provide direct benefit by reducing the severity of their illness as measured by duration of fever, risk of hospitalization, intubation or death.

Fo-Tv can potentially accelerate, prolong, or enhance the quality of immune responses to vaccine antigens and improve the efficacy of vaccines in individuals with reduced or weakened immune responses as measured by laboratory testing and/or reduce severity of vaccine side effect profile as measured by symptoms scoring.

It is also possible that there may not be any direct benefit for study participants.

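### Sub-studies 1a/1b: scheduled temperature readings stop after two consecutive afebrile values and resume only at day 14, so a new or returning fever on treatment is not scheduled to be measured

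*Combined protocol and SAP*

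**What the plan says.** Section 9, under Sub-studies 1a and 1b, says participants are "asked to take their temperature twice daily until they reach two consecutive afebrile readings". The Vital Signs item of the Clinical Assessments gives a different frequency with the same stopping condition: "daily throughout the treatment period until two consecutive afebrile results are seen, and again at the End of Study Treatment Day 14". Treatment is "8 capsules three times a day for 14 consecutive days". After day 14, temperature follow-up is kept only for non-hospitalised participants who are still febrile and symptomatic at that visit.

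Entry to 1a requires "Positive COVID-19 diagnosis within the prior 72 hours or within 9 days of symptom onset", and the criterion for 1b is the same. No inclusion or exclusion criterion for either sub-study mentions temperature. The temperature sections define no threshold for an afebrile reading and give no instruction to restart readings before day 14.

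Safety is a primary objective of both sub-studies (sections 6 and 9). For FoTv, section 14 quotes an FDA comment: "we are concerned these products may accelerate the development or exacerbate the magnitude of COVID-19". The protocol's reply ends: "We have relied on the Phase 1 safety study to monitor for any adverse effects that may result from FoTv administration". Section 17 describes possible benefit as "reducing the severity of their illness as measured by duration of fever, risk of hospitalization, intubation or death", and section 18 says much the same.

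**The concern.** The stopping rule suits a participant whose fever resolves once and stays away. It does not suit one who is afebrile at the start and becomes febrile later, or one whose fever subsides and returns. In both cases the thermometer record has closed before the event.

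This matters because little else is measured objectively during treatment. The other home measurements in the Vital Signs section apply only to participants with hypertension, diabetes, heart failure or diuretic use. For everyone else, temperature is the only scheduled home vital sign. Once it stops, the only objective sample before day 14 is the day-7 nasal swab or saliva sample, because safety bloods are drawn at baseline and day 14. In 1a the protocol answers the exacerbation concern by pointing to monitoring in this phase, so a gap in the on-treatment record weakens that answer.

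**Working it through.** The documents give no figure on this point, so there is none to reproduce. The check counts scheduled readings.

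**Inputs.** Treatment lasts 14 days (Test Product Dose and Route of Administration). Readings are twice daily (section 9) or daily (Vital Signs). They stop after two consecutive afebrile values (both places). One further reading is due at day 14 (Vital Signs).

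**Entrant afebrile from the start, twice-daily schedule.**
- A full record would be 14 × 2 = 28 readings.
- The rule is met on day 1. Scheduled readings are two on day 1 and one on day 14, so 3 of 28.
- Days 2-13 have none: 12 of 14 days, 12/14 = 86%.

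**Same entrant, daily schedule.**
- A full record would be 14 readings.
- The rule is met on day 2. Scheduled readings fall on days 1, 2 and 14, so 3 of 14.
- Days 3-13 have none: 11 of 14 days, 11/14 = 79%.

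**Entrant febrile at the start.** If the second consecutive afebrile reading falls on day k (before day 14), days k+1 to 13 have no scheduled reading, which is 13 − k days. Setting k = 1 or k = 2 returns the 12 and 11 days above.

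**How much the day-14 reading recovers.** This step needs assumptions that the documents do not supply: a fever lasting L whole days, with onset equally likely on any unmeasured day. Day 14 then catches it only if onset is on day 15 − L or later. That is L − 1 of the 12 (or 11) possible onset days.

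| Fever length | Twice-daily schedule | Daily schedule |
|---|---|---|
| 1 day | 0/12 = 0% | 0/11 = 0% |
| 3 days | 2/12 = 17% | 2/11 = 18% |
| 5 days | 4/12 = 33% | 4/11 = 36% |
| 7 days | 6/12 = 50% | 6/11 = 55% |

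The choice between the two stated frequencies hardly changes the result. The stopping condition creates the gap.

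**The case against.** The strongest reply is that exacerbation is watched by other means. Participants score COVID-19 symptoms in a daily diary, coordinators review symptoms daily, and the medical monitor reviews them daily during treatment (section 15). There is a 24-hour physician line, escalations of care are captured, and day-14 CRP, ferritin, D-dimer, LDH and troponin can be set against baseline. This stands. A reader might infer that a fever between the early readings and day 14 would go undetected, and the documents do not support that. What is lost is the measurement: such a fever would be unquantified and would depend on the participant noticing it. The backstop is also less firm for participants without email. The Symptoms item has them contacted daily, while section 9 allows paper-diary data to be reported at study completion.

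A second reply is that the diary asks for temperature and everyone has a thermometer, so some may keep recording. That also stands. The counts above are the minimum the schedule requires, not a forecast of missing data.

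A third reply concerns analysis. A reader might infer that a product which lowers fever and then lets it rebound would look favourable. The documents do not support this for 1a/1b. Fever duration appears only in the benefit and risk/benefit narrative. It is not among the aims, and the statistical section plans no comparison of it.

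Finally, the FDA comment names FoTv only and speaks of excessive immune response, not fever. It cannot be carried over to mQFPD in 1b. The 5-7 day pre-admission window in the background section also adds little. It describes patients who were later hospitalised, and entrants may be up to 9 days past symptom onset.

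**Conclusion.** The gap is real and follows directly from the schedule. An entrant who is afebrile at the start has 12 of 14 treatment days (twice-daily) or 11 of 14 (daily) with no scheduled temperature, and a relapse after two afebrile readings is likewise not scheduled to be measured. These are figures for one such participant. They should not be read as a trial-wide loss of data, because the documents do not give the share of entrants who would be afebrile.

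The consequence is limited. The objective on-treatment safety record is weaker than it needs to be in both sub-studies. In 1a it is also part of what the protocol relies on to answer the exacerbation concern. No planned 1a/1b endpoint, error rate or sample size is affected. Fever duration, which the protocol names as a measure of benefit, could not be computed reliably from this record if anyone later wished to use it. The point is a worthwhile low-cost improvement and does not amount to a flaw that undermines the sub-studies.

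**What to change.** Three edits, all to data collection or tabulation:

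1. Reconcile the reading frequency between section 9 (twice daily) and Vital Signs (daily), and state one frequency in both places.
2. Remove the early-stop condition in both places, so that every 1a/1b participant who is not hospitalised records temperature through day 14 in the existing diary.
3. Add to the safety tabulations a count by arm of participants with new or recurrent fever after an afebrile period, with the threshold for fever stated.

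Thermometers and a diary with a temperature field already go to every 1a/1b participant, so no equipment is added. The burden for an entrant afebrile throughout is at most 28 − 3 = 25 further readings on a twice-daily schedule, or 14 − 3 = 11 on a daily one. Some of these will be missed. Dosing, clinical management and sample size do not change.

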### **Sub-study 1c**

Once enrolled, all study participants will receive a package containing the following:

- Four day supply of study medication (capsules containing either FoTv or placebo)
- 
- Written instructions on proper usage of study medication
- Paper study daily diary, to include daily medication diary, symptom scores, and temperature/BP measurement data

During the trial period, participants will be verbally instructed on proper usage of study product and to assess their symptoms. Each participant will receive a paper copy and an emailed study daily diary to record symptoms and symptom scores, medication compliance, and any other medication use.

Participants will be asked to report to the study team any adverse events, either of the study medication or of the vaccination itself, including urgent care, emergency room, or hospitalization.

Subjects will be contacted by phone by the study team 2 weeks after vaccination # 1, 4 weeks after vaccination # 1, 2 weeks after vaccination # 2 (if applicable), 4 weeks after vaccination # 2 (if applicable), 6 months after baseline, and 12 months after baseline to report any symptoms.

### **Clinical Assessments:**

#### **1. Demographics**

Demographic information (name, age, gender, race/ethnicity, address, contact and emergency contact) will be recorded at Screening

#### **2. Medical History**

A targeted medical history, including history of current bleeding disorders, kidney disease, liver disease, immunocompromised status, and pregnancy/lactation status will be recorded at Screening. Updated medical history including medication reconciliation and adverse effects, will be recorded at:

- Baseline, Study Treatment Days 1 and 14, and at Study Days 28 and 58 for sub-studies 1a and 1b; or
- Baseline, 2 weeks after vaccination # 1, 4 weeks after vaccination # 1, 2 weeks after vaccination # 2 (if applicable), 4 weeks after vaccination # 2 (if applicable), 6 months after baseline, and 12 months after baseline (for sub-study 1c).

### 3. Concomitant Medications

All concomitant medication and concurrent therapies will be documented at

- Baseline/Screening Visit 1, Day 14 EOT visit, Day 28 Follow-up visit, and Day 58 EOS visit for sub-studies 1a and 1b; or
- Baseline, 2 weeks after vaccination # 1, 4 weeks after vaccination # 1, 2 weeks after vaccination # 2 (if applicable), 4 weeks after vaccination # 2 (if applicable), 6 months after baseline, and 12 months after baseline (for sub-study 1c)

Dose, route, unit frequency of administration, and indication for administration and dates of medication will be captured.

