#### A. Safety:

The following safety data will be collected and assessed during the study:

- 1) Incidence and severity of adverse events
- 2) Laboratory evaluations
- 3) Home glucometer measurements for diabetic participants
- 4) Home blood pressure measurements for hypertensive participants
- 5) Home daily weight measurements for patients with congestive heart failure or diuretic use

Safety data will be collected and assessed using the following methods:

- 1) Each participant will receive a paper copy and an emailed daily diary requesting information on symptoms (including duration and severity), vitals, and medication compliance. Participants who are unable to respond to emails will be asked to directly record this data into the provided paper study daily diary and then will be contacted daily to report this information to the study coordinator. All email exchanges among study personnel will be conducted within the UC intranet secure system. All communications with patients will be through virtual appointments using UC secure systems, UC San Diego encrypted emails or with password-protected study documents.
- 2) Study coordinators will collect and enter all safety data. All serious adverse events (SAEs) will, per UCSD IRB guidelines, be reported to the IRB and DSMB within 3 business days of learning of the event. Any adverse events, as well as any escalation of care, including urgent care, emergency room, or hospitalization, will be reported to the study team after appropriate medical care has been received, via a dedicated phone number or email address that is specific for urgent matters.
- 3) The UCSD site will implement a Data and Safety Monitoring Board (DSMB) to review data safety and monitoring as part of their responsibilities. The DSMB will include two senior researchers and a consumer representative. They will have conference calls bi-weekly (or more frequently, if needed)
- 4) The study biostatistician will send a tabulated symptom and adverse event report daily to all sites and to the study PI and weekly to the study DSMB and IRB.
- 5) The safety of the study medication will also be assessed through laboratory data collection at baseline, and at either the end of the treatments following end of quarantine (for non-hospitalized patients) or as part of hospital admission labs (for patients requiring hospitalization)
  - e. Basic Metabolic Panel
  - f. Complete Blood Count with Differential
  - g. Liver Function Testing

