## **9. RESEARCH DESIGN AND METHODS**

The following research design applies to each of the following studies:

Sub-study 1a: FoTv vs. placebo for acute COVID-19 patients

Sub-study 1b: QFPD vs. placebo for acute COVID-19 patients

Sub-study 1c: FoTv vs. placebo as an adjunct to COVID-19 vaccination

Sub-studies 1a and 1b of Phase 1 trial will each be 2-arm multicenter double blind randomized placebo controlled clinical trials.

Each of these safety/feasibility sub-studies will be conducted identically with the exception of additional exclusion criteria that will be required for sub-study 1b on account of the presence of herbal components including ephedrine that require these precautions for avoiding herb-drug interactions.

Sub-study 1c will be a single site double blind randomized placebo controlled clinical trial.

This will be a shorter intervention with broader inclusion criteria.

The research design and methods for the larger efficacy trial (Phase 2) will require analysis of these first two feasibility studies, and the final protocol will be submitted as a future amendment.

The primary objective of sub-studies 1a and 1b will be to assess the safety of FoTv or mQFPD, respectively, when used as therapies for acute COVID-19 infection and feasibility of the study protocol.

The primary objectives of sub-study 1c will be to ascertain the safety of FoTv when used as an adjunct to standard COVID vaccination as well as to evaluate its effects on post-vaccine COVID-19 antibody titers and on vaccination-related side effects.

A total of 66 subjects (33 FoTv or mQFPD and 33 placebo) will be enrolled in each of the 1a and 1b sub-studies.

A total of 266 subjects (133 FoTv and 133 placebo) will be enrolled in sub-study 1c.

The study protocol will be implemented and safety, feasibility, clinical, and laboratory data will be collected.

Interested participants will be asked to contact the study team, who will then conduct screening, consenting, and study enrollment. The study will be open to patients who are

- a) Mildly-to-moderately symptomatic and have tested positive for COVID-19 (sub-studies 1a and 1b)
- b) Scheduled for COVID-19 vaccination (sub-study 1c).

See section 11 for recruitment plan.

Once their eligibility has been confirmed, participants will be randomized to one of two groups by the study statistician:

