Each participant will receive a paper copy and an emailed study daily diary requesting this information (temperature readings, blood pressure and/or glucometer readings) as well as symptom scores, and medication compliance. This survey (daily diary) will be generated directly through the study database and will interface directly with the secured study database. Participants who are unable to respond to emails will be allowed to record data into the provided paper diary and report the information at the completion of the study to a member of the study team by phone or photo at intervals specified below. Once this information has been reported, there will be no need for the study team to collect the diary.

Any adverse events, as well as any escalation of care, including urgent care, emergency room, or hospitalization, will be reported to the study team after appropriate medical care has been received, via a dedicated phone number or email address that is specific for urgent matters. A dedicated phone number will be available throughout the entire study period to call a physician member of the study team who is available 24 hours a day, 7 days per week, for urgent matters. Non-urgent messages will be routed to a dedicated email address or study coordinator.

If a study participant is hospitalized as a result of COVID-19, the participant will be instructed to discontinue study medication and the study team will follow up with either the patient or the emergency contact at the end of the trial period, or following the hospitalization, to determine final outcome and obtain laboratory records from the hospitalization.

At Day 14, a telephone call will be conducted among participants who have not been hospitalized to assess for COVID-19 symptoms, review any adverse events, review concomitant medications, drug accountability (participants will take pictures of

their empty bottles and send to the study team), and harmonize any data discrepancy between their daily diary and the study database. At this time, they will have completed the investigational product.

At the time of the Day 14 telephone call, participants who have not been hospitalized will be directed to obtain end-of-trial blood draw via outpatient laboratory or in-home phlebotomy.

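### Sub-study 1b states its interacting drugs only as entry exclusions and schedules no medication review on Days 2 to 13 of the 14 dosing days

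*Combined protocol and SAP*

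**What the plan says.** Section 9 says that sub-studies 1a and 1b will be "conducted identically with the exception of additional exclusion criteria that will be required for sub-study 1b", and gives as the reason "herbal components including ephedrine that require these precautions for avoiding herb-drug interactions". The drugs are listed in Section 10 under the sub-study 1b Exclusion Criteria: anticoagulation (9), named drugs or classes including systemic corticosteroids and digoxin (10 to 17), monoamine oxidase inhibitors (19), methamphetamine and cocaine in the 30 days before entry (20 and 21), and a closing group that includes lithium, theophylline and warfarin (22). Nothing there says that the criteria continue to apply once dosing starts.

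On timing, the Concomitant Medications section documents medication at "Baseline/Screening Visit 1, Day 14 EOT visit, Day 28 Follow-up visit, and Day 58 EOS visit for sub-studies 1a and 1b" and says that "indication for administration and dates of medication will be captured". The Medical History section updates the history, including medication reconciliation, at "Baseline, Study Treatment Days 1 and 14, and at Study Days 28 and 58 for sub-studies 1a and 1b". The Day 14 telephone call includes a medication review, and of that moment the protocol says: "At this time, they will have completed the investigational product".

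The 1a/1b diary is described as collecting vitals, symptoms, possible side effects and adherence to study product. The 1c diary is described as also recording other medicines taken. Section 14, under mQFPD risk, says interactions are handled by the exclusions together with safety monitoring, and names daily blood pressure in hypertensive participants as an example.

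**The concern.** Safety of mQFPD is a primary objective of 1b, and the extra exclusions exist to prevent herb-drug interactions. A combination judged unacceptable at entry is no more acceptable on Day 5, yet the precaution as written stops at entry. New prescriptions are foreseeable: participants have symptoms when they enter, and the Adverse Events section refers reported COVID-19 symptoms to the primary care provider.

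What is at stake is the chance to act. If a listed drug first comes to light at the Day 14 call, the medical monitor can no longer decide whether mQFPD should be stopped. Later attribution suffers less, because dates of medication and of adverse events are both recorded and can be lined up.

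**Working it through.** The plan gives no figure of its own on this point. The check compares the schedule with the dosing period and then looks at what each daily contact is said to ask.

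**Schedule.** Dosing lasts 14 consecutive days (Section 9, Test Product Dose). Medication reviews within dosing fall on Day 1 (Medical History) and Day 14 (Medical History, Concomitant Medications, Day 14 call). Days without one: 2 to 13, that is 13 − 2 + 1 = 12 of 14.

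**Overlap.** For an outpatient who starts a listed drug on day d and is not picked up by another route, dosing days with both products = 15 − d.
- d = 2: 15 − 2 = 13 days
- d = 13: 15 − 13 = 2 days
- with a daily question: about 1 day

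The longest recall at the Day 14 call is 14 − 2 = 12 days, a modest limitation.

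**Daily contacts in 1a/1b as described.**

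| Contact | Stated content | Asks about new medicines? |
|---|---|---|
| Daily diary (Section 6; Section 9, Sub-studies 1a and 1b; Symptoms) | vitals, symptoms, side effects, adherence to study product | not stated |
| Daily coordinator contact (Adverse Events) | symptoms and their severity | not stated |
| Daily medical-monitor review (Section 15) | recorded symptoms | not stated |
| Home blood pressure, glucose, weight (Vital Signs) | readings, only with the relevant baseline condition or drug | no |

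**Possible count.** The documents give no rate of new listed drugs. Assume that a proportion p of the mQFPD arm starts one on Days 2 to 13, independently. Expected starts = n × p; chance of at least one = 1 − (1 − p)^n.

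| p (assumed) | Expected, n = 33 | Chance of at least one, n = 33 | Chance of at least one, n = 27 |
|---|---|---|---|
| 0% | 0 | 0% | 0% |
| 1% | 0.33 | 28% | 24% |
| 2% | 0.66 | 49% | 42% |
| 5% | 1.65 | 82% | 75% |

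Here n = 33 is the enrolled arm and n = 27 the arm net of the planned allowance for dropout. These are chances that someone starts a listed drug, not that the start goes unnoticed or does harm.

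**The case against.** The strongest reply is that the diary may already ask. The package lists for 1a/1b and for 1c describe the paper diary in the same words, including a daily medication diary. The 1c line even mentions temperature and blood pressure, although the Vital Signs section limits those to 1a and 1b. That suggests a shared form, and the 1c text says its diary records other medicines. The diary form, the written usage instructions, the consent form and Appendix 1 are not in the supplied text, and any of them might tell participants to report new drugs. This stands as a real uncertainty. It does not settle the matter: the only use the 1a/1b text states for the medication diary is logging missed doses, and a shared form would still supply no on-treatment ban or stopping rule.

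The second reply is that other safeguards would expose most new drugs. Escalations of care, including urgent care and emergency visits, must be reported. Coordinators are in daily contact, the medical monitor reviews symptoms daily, and a physician line runs around the clock. Cardiac or pulmonary deterioration is escalated at once. Hospitalization for any reason, a skin eruption or an asthma-type exacerbation stops dosing. The team holds primary care contact details, and under the chart-review route the physician is told of participation. This also stands, and it shrinks the gap considerably. None of these provisions is said to ask about a new drug, and a routine prescription need not trigger any of them.

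A reader might infer that 1b has no protection against interactions after entry, or that a new drug would necessarily stay hidden until Day 14. The provisions above contradict both readings.

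**Conclusion.** The point holds in a limited form. As written, 1b schedules no medication review on 12 of 14 dosing days, does not extend its drug exclusions into dosing, and has no rule for an outpatient who starts a listed drug. The remaining exposure is a listed drug begun at a routine outpatient visit and not volunteered in daily contact. Such a case could run for 2 to 13 dosing days before the first scheduled question.

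The expected count is small: 0 to 1.7 starts under assumed rates of 0% to 5%, with some of these caught or cut short by existing safeguards. The conclusion rests on the protocol text and would soften if the 1a/1b diary form already asks about other medicines. A reader might also take the percentages above as the risk of undetected overlap or harm, or conclude that the safety analysis is biased. The documents support neither: the start rates are assumptions, and drug and event dates are recorded. The change is still worth making, because it concerns participant safety and costs little.

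**What to change.** 1. In the sub-study 1b Exclusion Criteria, state that the drug criteria (the anticoagulation part of 9, then 10 to 17 and 19 to 22) apply throughout the 14 dosing days. For 20 and 21, which look back 30 days at entry, this means no use during dosing.
2. Add the 1c item on other medicines, with name and start date, to the 1b daily diary, and have coordinators ask it in the daily contact that already exists. If the form already contains the item, say so in the protocol.
3. Send any match to the medical monitor the same day, in both arms and without unblinding, to decide whether study product should stop. Needed treatment is not withheld.
4. As a secondary matter, settle how paper-diary users report, so that the new item reaches the team in time. Section 9 has them "report the information at the completion of the study to a member of the study team by phone or photo at intervals specified below", whereas Section 6 has them "contacted daily to report this information to the study coordinator". The daily version is the one needed.

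The cost is one diary item, one question in an existing contact, one database flag and a few sentences of protocol text. The downside is slight extra burden for participants and coordinators, and possibly a few early stops of study product.
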